 - MTX 15 to 25 mg/week. If the current MTX dose is < 15 mg/week, the subject's intolerance to ≥ 7.5 mg dose must be documented in the subject's medical history
 - ≤ 3000 mg/day (3 g/day) sulfasalazine

- ≤ 400 mg/day hydroxychloroquine
- ≤ 200 mg/day minocycline
- ≤ 20 mg/day leflunomide

*Note: Combinations of up to 2 csDMARDs are allowed. However, combination of MTX and leflunomide is not allowed. Subjects are allowed to continue taking csDMARDs therapy at stable doses (initiated ≥ 4 weeks prior to the first dose of study drug) throughout the study period.

- a) If subjects have to discontinue csDMARDs therapy (except for leflunomide), the washout windows of 30 days prior to Day 1 dosing must be observed.
- b) If subjects have to discontinue leflunomide due to combination use with MTX before enrollment, the following washout windows must be observed: subjects who discontinued leflunomide and have had successful chelation with 8 g of cholestyramine (3 times daily) for 3 days must wait for 4 weeks prior Day 1 dosing. Subjects who discontinued leflunomide and did not have cholestyramine washout must wait 12 weeks after last dose of leflunomide prior to Day 1 dosing.

5. Subject taking MTX while on study must be willing to take dietary supplement of oral folic acid (or equivalent, such as folinic acid) at a stable dose.
6. Subject who has adequate renal and hepatic function at screening as defined by the following clinical chemistry results:
 - a. Serum creatinine $< 1.5 \times$ ULN or an estimated creatinine clearance level ≤ 50 mL/min (by MDRD GFR equation)
 - b. Serum alanine aminotransferase $< 2.5 \times$ ULN
 - c. Serum aspartate aminotransferase $< 2.5 \times$ ULN
 - d. Serum total bilirubin $< 2 \times$ ULN

Repeat of clinical chemistry laboratory tests may be allowed once during screening period (after an approval from medical monitor), if the initial result is unexpected/unexplained (not due to a known underlying condition or concomitant medications or other known cause).

7. Subject who has the following hematology laboratory test results at screening:
 - a. Hemoglobin ≥ 8.5 g/dL (International System of Units [SI] units: ≥ 85 g/L or 5.28 mmol/L)
 - b. White blood cell count $\geq 3.5 \times 10^3$ cells/ μ L (SI units: $\geq 3.5 \times 10^9$ cells/L)
 - c. Neutrophil count $\geq 1.5 \times 10^3$ cells/ μ L (SI units: $\geq 1.5 \times 10^9$ cells/L)
 - d. Platelet count $\geq 100 \times 10^3$ cells/ μ L (SI units: $\geq 100 \times 10^9$ cells/L)

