4.1 Selection of Study Population

Approximately 148 subjects will be enrolled at multiple sites in the United States, Europe, and South Korea. Subjects will be assigned to study treatment only if they meet all of the inclusion criteria and none of the exclusion criteria.

Deviations from the inclusion and exclusion criteria are not allowed because they can potentially jeopardize the scientific integrity of the study, regulatory acceptability, or subject safety. Therefore, adherence to the criteria as specified in the protocol is essential.

If a subject fails one or more inclusion or exclusion criteria, one re-screening attempt is allowed per subject.

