*Note: Combinations of up to 2 csDMARDs are allowed. However, combination of MTX and leflunomide is not allowed. Subjects are allowed to continue taking csDMARD therapy at stable doses (initiated \geq 4 weeks prior to the first dose of study drug) throughout the study period.

a) If subjects have to discontinue csDMARD therapy (except for leflunomide), the washout windows 30 days prior to Day 1 dosing must be observed.

b) If subjects have to discontinue leflunomide due to combination use with MTX before enrollment, the following washout windows must be observed: subjects who discontinued leflunomide and have had successful chelation with 8 g of cholestyramine (3 times daily) for 3 days must wait for 4 weeks prior Day 1 dosing. Subjects who discontinued leflunomide and did not have cholestyramine washout must wait 12 weeks after last dose of leflunomide prior to Day 1 dosing.

5. Subjects taking MTX while on study must be willing to take dietary supplement of oral folic acid (or equivalent, such as folinic acid) at a stable dose.
6. Subject who has adequate renal and hepatic function at screening as defined by the following clinical chemistry results:
 - a. Serum creatinine $<1.5 \times \text{ULN}$ or an estimated creatinine clearance level $\leq 50 \text{ mL/min}$ (by MDRD GFR equation)
 - b. Serum alanine aminotransferase (ALT) $<2.5 \times \text{ULN}$
 - c. Serum aspartate aminotransferase (AST) $<2.5 \times \text{ULN}$
 - d. Serum total bilirubin $<2 \times \text{ULN}$.

Repeat of clinical chemistry laboratory tests may be allowed once during screening period (after an approval from medical monitor), if the initial result is unexpected/unexplained (not due to a known underlying condition or concomitant medications or other known cause).

7. Subject who has the following hematology laboratory test results at screening:
 - a. Hemoglobin $\geq 8.5 \text{ g/dL}$ (International System of Units [SI]: $\geq 85 \text{ g/L}$ or 5.28 mmol/L)
 - b. White blood cell count $\geq 3.5 \times 10^3 \text{ cells}/\mu\text{L}$ (SI units: $\geq 3.5 \times 10^9 \text{ cells/L}$)
 - c. Neutrophil count $\geq 1.5 \times 10^3 \text{ cells}/\mu\text{L}$ (SI units: $\geq 1.5 \times 10^9 \text{ cells/L}$)
 - d. Platelet count $\geq 100 \times 10^3 \text{ cells}/\mu\text{L}$ (SI units: $\geq 100 \times 10^9 \text{ cells/L}$).

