5. Subject who has any condition that could confound the evaluation of the data or the effect of the study drug, such as:

- a. Any other inflammatory or rheumatic diseases, including but not limited to psoriatic arthritis, ankylosing spondylitis, spondyloarthritis, systemic lupus erythematosus, Lyme disease, or uncontrolled fibromyalgia. Subjects with inactive or well-controlled fibromyalgia will be allowed to be enrolled in this study if the disease does not impact the study assessments, as per the investigator's judgement. Subjects with Sjogren's disease secondary to RA are eligible.
- b. Any conditions significantly affecting the nervous system (ie, neuropathic conditions or nervous system damage) if it may interfere with the investigator's assessment on DAS including joint counts.
- c. Severe physical incapacitation (unable to perform routine self-care, has RA ACR functional status class 4 [Arnett et al 1988], or who cannot benefit from medication).
- d. Any other serious acute or chronic medical or psychiatric condition that may increase the risk associated with study participation or study drug administration or that may interfere with the interpretation of study.

6. Subject who currently has one or more of the following medical conditions which in the opinion of the investigator would put the subject at risk by participating in the protocol:

- a. Uncontrolled diabetes mellitus, even after insulin treatment.
- b. Uncontrolled hypertension (as defined by systolic blood pressure ≥ 160 mm Hg or diastolic blood pressure ≥ 100 mm Hg on >1 occurrence or as judged by the investigator).
- c. Clinically significant finding meeting any protocol exclusion criteria on chest x-ray. Chest x-ray must be obtained during the screening period, unless a radiograph lung imaging (ultrasound not acceptable) was obtained within 12 weeks prior to the screening visit.
- d. Evidence of cardiac conditions as defined by the following:
 - New York Heart Association (NYHA) class III or IV heart failure, severe uncontrolled cardiac disease (unstable angina), or myocardial infarction within the 6 months prior to Day 1.

- Clinically relevant or significant ECG abnormalities, including ECG and QT interval correction for heart rate (QTc) using Fridericia's correction formula (QTcF). Subject with prolonged QT interval (using QTcF) defined as QTc >450 ms for male and >470 ms for female at retest will be excluded at screening.

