4.2 Withdrawal of Subjects From the Study Treatment and/or the Study

4.2.1 Reasons for Withdrawal/Discontinuation

Subjects may withdraw from the study at any time and for any reason without prejudice to their future medical care by the investigator or at the study site. Every effort should be made to keep subjects in the study. The reasons for subjects not completing the study will be recorded.

A subject may be withdrawn from the study for any of the following reasons:

1. Noncompliance with the protocol.
 - Protocol violations may result in data that are not deemed evaluable (by the investigator) for a protocol analysis and/or may require subject(s) to be discontinued.
2. Pregnancy.
 - If a female subject becomes pregnant, she must discontinue study drug immediately.
3. A serious or intolerable adverse event(s) (AE[s]) that in the Investigator's opinion requires withdrawal from the study.
 - Upon occurrence of a serious or intolerable AE that in the investigator's opinion requires withdrawal from the study, the investigator will confer with the sponsor.
 - If a subject is discontinued because of an AE, the event will be followed until it is resolved.
4. Laboratory safety assessments that reveal clinically significant hematological or biochemical changes from the baseline values.
5. Symptoms or an intercurrent condition not consistent with the protocol requirements or that justifies withdrawal (eg, development of contraindications of use of study drug).
6. Lost to follow-up.
 - Subjects that are considered lost to follow-up, reasonable attempts must be made to obtain information on the final status of the subject.

- At a minimum, 2 phone calls must be made and 1 certified letter must be sent for documentation.

7. Death of the subject.
8. Early termination of the study by the sponsor.
9. The subject withdraws consent.

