Chemistry: bicarbonate, bilirubin (total and direct), blood urea nitrogen, calcium, chloride, cholesterol (total, high-density lipoprotein, and calculated low-density lipoprotein), creatine phosphokinase, creatinine, gamma-glutamyltransferase, globulin, glucose, lactate dehydrogenase, magnesium, phosphorus, potassium, sodium, total protein, triglycerides, troponin I, uric acid, and C-reactive protein

Urinalysis: Appearance, bilirubin, color, glucose, ketones, leukocyte esterase, microscopy (performed if dipstick is positive; includes bacteria, casts, crystals, epithelial cells, red blood cells, and white blood cells), nitrites, occult blood (for urine microscopy), pH, protein, specific gravity, and urobilinogen

Pregnancy: Urine dipstick pregnancy test except at screening

In cases of abnormal urinalysis results, urine microscopy will be performed.

Abnormal clinical laboratory values will be flagged as either high or low (or normal or abnormal) based on the reference ranges for each laboratory parameter. The Investigator will determine whether any abnormally high or low results are clinically significant or not clinically significant. Clinical significance is defined as any variation in results that has medical relevance and may result in an alteration in medical care (eg, active observation, diagnostic measures, or therapeutic measures).

If a clinically significant change from the screening value is noted, the clinically significant value and the reason for clinical significance will be documented on the AE page of the subject's eCRF, even if asymptomatic. The Investigator will continue to monitor the subject with additional assessments until the values have reached either the reference range or the values at screening or until the Investigator determines that follow-up is no longer medically necessary.

The US Food and Drug Administration (FDA) guidance for industry on Drug-Induced Liver Injury: Premarketing Clinical Evaluation (July 2009) will be used as a guideline for the assessment of liver enzymes/liver function tests (DHHS 2009).

Clinically significant laboratory values for individual subjects will be listed. A summary for the numbers and percentages of subjects with clinically significant laboratory values at any time point will be presented.

All laboratory specimen (clinical and bioanalysis) analysis, details in storage and shipment will be followed according to the laboratory manual.

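### Inclusion criterion 6a has its clearance sign reversed: once creatinine reaches 1.5 × ULN, low estimated clearance is what qualifies a subject as having adequate renal function

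*Protocol*

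**What the plan says.** Criterion 6 in Protocol Section 4.1.1 is introduced as "Subject who has adequate renal and hepatic function at screening as defined by the following clinical chemistry results". Its renal part, 6a, has two limbs joined by 'or': serum creatinine below 1.5 × ULN, "or an estimated creatinine clearance level ≤ 50 mL/min (by MDRD GFR equation"). The Synopsis and Section 4.1.1 carry the same wording and the same sign.

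The limits next to it are written as one would expect. Creatinine, ALT, AST and bilirubin have upper limits. Criterion 7 sets floors, for example "Hemoglobin ≥ 8.5 g/dL".

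A subject must meet every inclusion criterion to enrol. Section 4.1 allows no deviations and says that "adherence to the criteria as specified in the protocol is essential". The nearest other entry safeguard is exclusion 5d in Section 4.1.2: "Any other serious acute or chronic medical or psychiatric condition that may increase the risk associated with study participation or study drug administration". It contains no renal threshold.

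**The concern.** An inclusion limit meant to secure adequate renal function should be a floor on clearance. Here it is a ceiling. Because the limbs are joined by 'or', a subject who fails on creatinine is rescued by having low clearance, and a subject with the same creatinine and better clearance is turned away.

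What is at stake is patient safety at entry. Criterion 6a is the only numeric renal screen in the protocol. Previous human safety experience is described in healthy subjects (Sections 1.1 and 1.3). The 400 mg BID dose had not been given to humans before, and predicted exposure to metabolite M4 at that dose is above the NOAEL exposure, although the protocol expects it to stay within levels already seen in volunteers at 800 mg (Section 1.3). There is no safety monitoring committee and no external data monitoring committee (Sections 6.7 and 11.1.1).

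Several on-study rules look for change, so they would not pick up impairment that was present at entry and stayed stable:

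- The laboratory reason for withdrawal in Section 4.2.1 is "Laboratory safety assessments that reveal clinically significant hematological or biochemical changes from the baseline values".
- The laboratory adverse-event rule in Section 6.4.4 begins "If a clinically significant change from the screening value is noted".
- The shift tables in SAP Section 9.3 start from the baseline grade.

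**Working it through.** No power or sample size figure is involved. The check treats 6a as a logical rule.

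**Inputs** (Protocol Synopsis and Section 4.1.1, criterion 6a): creatinine limit 1.5 × ULN; clearance limit 50 mL/min; connector 'or'.

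**Rules compared.** Let A mean creatinine < 1.5 × ULN, and CL the estimated clearance in mL/min.

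- As written: pass if A or CL ≤ 50.
- Sign reversed: pass if A or CL ≥ 50.

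| Creatinine (× ULN) | CL (mL/min) | A | As written | Sign reversed |
|---|---|---|---|---|
| 1.0 | 90 | true | pass | pass |
| 1.4 | 45 | true | pass | pass |
| 1.6 | 15 | false | **pass** (15 ≤ 50) | **fail** |
| 1.6 | 50 | false | pass (50 ≤ 50) | pass (50 ≥ 50) |
| 1.6 | 60 | false | **fail** | **pass** (60 ≥ 50) |

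The creatinine and clearance pairs are illustrations; how often each occurs is unknown. The two rules differ only when creatinine is ≥ 1.5 × ULN and clearance is not exactly 50. The subjects wrongly admitted are those with creatinine ≥ 1.5 × ULN and CL < 50.

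**Comparison with neighbouring limits.** Criterion 6 has five numeric limits (creatinine, clearance, ALT, AST, bilirubin) and criterion 7 has four (hemoglobin, white cells, neutrophils, platelets), so 5 + 4 = 9. Eight keep out the unhealthy side. Only the clearance limit admits it.

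**Is it a reading error?** The sign is encoded differently in the Synopsis and in Section 4.1.1, yet both read as 'at most'. The 'at least' signs in criterion 7 came through correctly. A conversion fault is therefore unlikely.

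**Does another rule catch it?** Exclusion 6 covers diabetes, hypertension, chest x-ray findings, cardiac and respiratory disease, but nothing renal. Exclusion 5d is a matter of judgement. Table 3-1 has six trigger rows (ALT/AST/ALP, neutrophil count, blood pressure, nausea or vomiting, absolute QTcF, QTcF change), and none is renal.

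**The case against.** The strongest reply is that the error is real but its consequences are not shown.

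- **Size.** The sign matters only at creatinine ≥ 1.5 × ULN, and the number of such subjects cannot be derived. The potential risks named in Protocol Section 1.5 do not include a renal one, and much of the nonclinical text is not available. This stands: no renal hazard can be asserted or ruled out.
- **Entry safeguards.** A subject with raised creatinine and a clearance of 15 mL/min would naturally fall under exclusion 5d, and Section 11.2.2 implies sponsor approval before enrolment. Both lower the practical risk. Neither repairs a numeric rule that says the subject qualifies, and neither helps the subject with raised creatinine and better clearance whom the rule rejects.
- **Monitoring.** Not every rule is relative to baseline. Section 6.4.4 flags values against reference ranges and summarises clinically significant ones. SAP Section 9.3 lists all laboratory data with abnormality marked, and its shift tables show the baseline grade. Note a to Table 3-1 calls the rows examples and leaves other Grade 3/4 events to judgement. An abnormal entry creatinine would therefore be visible, but only after the subject has been admitted.
- **The remedy.** The documents do not state the intended sign or connector. With 'or' kept, creatinine below 1.5 × ULN still passes at any clearance, as the 1.4/45 row shows; only 'and' would close that. This stands, and it is why the medical team has to confirm both.
- **Nature of the fault.** It is plainly a drafting slip under a heading that shows the intent. True, but Section 4.1 tells sites to apply the criteria as they are written.

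**Conclusion.** The concern holds. As written, 6a works backwards whenever creatinine is at or above 1.5 × ULN: it admits clearance of 50 mL/min or less and rejects anything higher. It is the only one of nine limits in criteria 6 and 7 that does so, and the only numeric renal limit in the protocol.

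The existence of the error follows from the text alone and needs no assumption. That ≥ 50 mL/min was intended is an inference from the heading and the neighbouring limits. How many subjects were affected, and what harm could follow, cannot be determined from the documents. Below 1.5 × ULN the reversal changes nothing. The sample size and the primary ANCOVA are untouched. It should be corrected because it is an operative safety threshold and the correction is cheap.

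**What to change.** 1. In the Synopsis and in Section 4.1.1, change the clearance limit in 6a from ≤ 50 to ≥ 50 mL/min. Keep 'or' unless the sponsor's medical team decides that low clearance alone should exclude, in which case 'and' is needed. The team should also confirm ≥ rather than >; the choice affects only a subject at exactly 50.
2. From screening data, list for safety review every subject with creatinine ≥ 1.5 × ULN and estimated clearance ≤ 50 mL/min. A subject at exactly 50 passes both versions and can be marked as such.
3. Do not drop these subjects from the per-protocol set on this ground. Under SAP Section 4.5, exclusion rests on major protocol deviations or treatment non-compliance, and meeting the written criterion is neither.

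The cost is one sign in two places, by clarification letter or amendment, plus one listing. Creatinine is already in the chemistry panel (Section 6.4.4). Clearance is not itself on that panel, so the MDRD value would have to be derived from creatinine and the demographics collected under Section 6.2. No new assessment is needed and no analysis set changes. If enrolment has closed, which the documents do not show, only the listing still has value.

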HAQ-DI	health assessment questionnaire-disability index
anti-HBc	anti-hepatitis B core
HBsAg	hepatitis B surface antigen

Abbreviation	Definition
HCV	hepatitis C virus
HIV	human immunodeficiency virus
hsCRP	high sensitivity C-reactive protein
ICF	informed consent form
ICH	International Council for Harmonisation
IEC	independent ethics committee
IgE	immunoglobulin E
IGRA	interferon-gamma release assay
IND	investigational new drug
IRB	institutional review board
ITT	intention-to-treat
IxRS	interactive voice or web response system
K _{el}	terminal elimination rate constant
LOCF	last observation carried forward
MCP	metacarpophalangeal
MTX	methotrexate
MedDRA	Medical Dictionary for Regulatory Activities
mITT	modified intention-to-treat
NOAEL	no observed adverse effect level
NRI	nonresponder imputation
PCR	polymerase chain reaction
PD	pharmacodynamic(s)
PIP	proximal interphalangeal
PK	pharmacokinetic(s)
PP	per protocol
PVG	pharmacovigilance
QD	once daily
QTc	QT interval correction for heart rate
QTcF	QT interval correction for heart rate (QTc) using Fridericia's correction formula
RA	rheumatoid arthritis
R _{met}	metabolite ratio

Abbreviation	Definition
R _{AUC}	accumulation ratio based on AUC _{0-tau}
SI	International System of Units
SAE	serious adverse event
SJC	swollen joint count
SUSARs	suspected unexpected serious adverse reactions
SYK	spleen tyrosine kinase
t _{1/2}	apparent terminal elimination half-life
TB	tuberculosis
TJC	tender joint count
TEAE	treatment-emergent adverse event
TE _{max}	time to achieve maximum effect
T _{max}	time to reach the observed maximum (peak) concentration
TNF α	tumor necrosis factor alpha
ULN	upper limit of normal
US	United States
VAS	visual analog scale
V _{z/F}	apparent oral volume of distribution

1 Introduction

Rheumatoid arthritis (RA) is a chronic autoimmune polyarthritis that affects approximately 1% of the world's population (Lee and Weinblatt 2001), including 1.3 million people in the United States (Helmick et al 2008). Although RA is primarily a disease of the joints, it is a multisystem disease and other organ systems can be affected.

Treatment guidelines from the European League Against Rheumatism (EULAR) (Smolen et al 2014) and American College of Rheumatology (ACR) (Singh et al 2012) are similar: methotrexate (MTX), a nonbiologic disease-modifying antirheumatic drug, alone and in combinations with other agents, remains the mainstay of disease-modifying therapy for patients with RA. Biologic disease-modifying antirheumatic drugs, notably tumor necrosis factor alpha (TNF α) inhibitors due to their established efficacy and safety profiles, can reduce signs and symptoms of RA, induce a major clinical response, and provide protection against structural damage. A subset of patients has demonstrated an inadequate response to anti-TNF drugs, and some patients initially respond to anti-TNF therapy but experience a loss of efficacy over time. Despite recent advances, there is still a medical need for alternative RA treatments for patients with inadequate responses, who show intolerance to conventional nonbiologic therapies, such as MTX, or whose disease is refractory to treatment with biologic products, particularly widely used TNF inhibitors (Cohen et al 2006; Emery et al 2008; Smolen et al 2009).

Spleen tyrosine kinase (SYK) is a nonreceptor tyrosine kinase known to have a crucial role in immune receptor signaling. A number of studies have revealed that aberrant SYK activation is associated with diverse allergic disorders and antibody-mediated autoimmune diseases such as RA, asthma, and allergic rhinitis.

Spleen tyrosine kinase is broadly involved in regulating leukocyte immune function, principally by facilitating cellular activation in response to receptor engagement of an antigen or immune complex. Receptors that use SYK for signal transduction include the B-cell antigen receptor, Fc receptors, integrins, and members of the lectin and selectin families (Turner et al 2000; Mócsai et al 2002; Rogers et al 2005; Zarbock et al 2008). As such, specific inhibition of SYK has the potential to control B-cell antibody response to antigens as well as the downstream effector functions of mast cells, basophils, neutrophils, eosinophils, macrophages, dendritic cells, and platelets (Mócsai et al 2010). Targeting SYK therefore

represents a multifaceted approach to the modulation of immune function at several points of intervention, making it a potentially unique target for drug development (Coffey et al 2012).

The novel small-molecule SYK inhibitor SKI-O-592 (the free base of SKI-O-703) has demonstrated high selectivity and potency against SYK in a biochemical assay. For immunoreceptor activation linked to SYK, the effect of SKI-O-592 on the anti-inflammatory response consisting of TNF α , β -hexosaminidase, and cluster of differentiation (CD)69 expression was greater than the effects of first-generation SYK inhibitors (eg, R406) in several immune cell lines and in human primary cells. This anti-inflammatory activity was responsible for the selective inhibition of p-SYK (Y525/526), which led to the sequential inhibition of downstream effectors. More importantly, the inhibitory activity of SKI-O-592 was more potent than that of R406 in human CD14 $+$ monocytes (38 and 106 nM in half-maximal inhibitory concentration [IC_{50}], respectively). SKI-O-592 also inhibited CD69 expression in Ramos with an IC_{50} value of 189 nM and was more potent than R406, which had an IC_{50} value of 978 nM. Hence, excellent SYK selectivity of SKI-O-592 led to no inhibition of SYK-independent signal pathways, indicating that SKI-O-592 shows more potent anti-inflammatory activity to allow continuous administration of SKI-O-703 compared with the first-generation SYK inhibitors.

